2.8.4 Other safety data

2.8.4.1 ECG and cardiac imaging data

All available ECG related data will be listed.

2.8.4.2 Vital signs

Analysis in vital sign measurement using descriptive summary statistics for the change from baseline for each post-baseline visit will be performed. These descriptive summaries will be presented by vital sign and treatment group. Change from baseline will only be summarized for subjects with both baseline and post-baseline values and will be calculated as:

change from baseline = post-baseline value – baseline value

The number and percentage of subjects with newly occurring notable vital signs will be

presented. Clinically notable vital signs are provided in the table below

Table 2.8-4 Criteria for notable vital sign abnormalities

Vital sign (unit)	Notable abnormalities
Systolic blood pressure (mmHg)	>= 140 mmHg or < 90 mmHg
Diastolic blood pressure (mmHg)	>=90 mmHg or <60 mmHg
Pulse (bpm)	> 100 bpm or <60 bpm

2.9 Pharmacokinetic endpoints

Not applicable.

2.10 PD and PK/PD analyses

Not applicable.

2.11 Patient-reported outcomes

All HR-QoL variables will be evaluated based on FAS patients.

The secondary efficacy variables related to patient-reported outcomes are:

- Change from baseline in SF12
- Change from baseline in HAQ-DI

SF12

The change from baseline in SF12 at each time point till Week 16 will be analyzed by an analysis of covariance (ANCOVA) model with treatment (3 treatment groups), baseline SF12 score, methotrexate usage at baseline (yes, no), and body weight as explanatory variables. The least squares means of the three treatment groups, least squares mean differences between each dose of secukinumab and placebo, 95% confidence intervals for the difference between each dose of secukinumab and placebo, and p-values based on the fitted linear model will be reported.

The SF-12v2 score will be computed in the following steps:

- 1. Enter the data
- 2. Recode out-of-range item values as missing
- 3. Reverse score and/or recalibrate scores for four items
- 4. Compute raw case scores
- 5. Transform raw scale scores to 0-100

Table: Scale Items Aggregated and Range of possible Scores

SF-12v2 scale	Sum Final item values	Lowest possible raw scores	Possible raw score range
Physical functioning (PF)	Items 2a+2b	2	4
Role Physical (RP)	Items 3a+3b	2	8
Bodily Pain (BP)	Item 5	1	4
General Health (GH)	Item 1	1	4
Vitality (VT)	Item 6b	1	4
Social Functioning (SF)	Item 7	1	4
Role Emotional (RE)	Items 4a+4b	2	8
Mental Health (MH)	Items 6a+6c	2	8

Transformed scale = ((Actual raw score-lowest possible raw score)/Possible raw score range)*100

HAQ-DI

The HAQ-DI was developed by Stanford University and is one of the most widely used measures to assess the long-term influence of chronic disease on a subject's level of functional ability and activity restriction. The disability assessment component of the HAQ, the HAQ-DI, assesses a subject's level of functional ability and includes questions of fine movements of the upper extremity, locomotor activities of the lower extremity, and activities that involve both upper and lower extremities. There are 20 questions in eight categories of functioning including dressing, rising, eating, walking, hygiene, reach, grip, and usual activities. The stem of each item asks over the past week "Are you able to …" perform a particular task. Each item is scored on a 4-point scale from 0 to 3, representing normal (normal, no difficulty [0]), some difficulty (1), much difficulty (2), and unable to do (3).

The purpose of the HAQ-DI in this study is to assess the functional ability of patients with PsA.

Analysis of HAQ-DI total score will be analogous to the analysis of SF12 for all time points up to Week 16.

In addition, the following two binary variables will be analyzed:

• HAQ-DI response, where response = yes if HAQ-DI score ≤ 0.5).

• HAQ-DI MCID, where response = yes if HAQ-DI change from baseline <= -0.35). The above analysis will be done at each time point using a logistic regression model with treatment (3 treatment groups), methotrexate usage at baseline (yes, no), and body weight as explanatory variables. The odds ratios for each dose of secukinumab versus placebo, 95% confidence intervals for the odds ratios, and p-values based on the fitted model will be reported.

In addition, number and percentages will be provided for HAQ-DI responders by treatment group at each visit for entire treatment period. Similar analysis will be performed using non-responder imputation.

U NOVARTIS

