4.1 Inclusion criteria

Patients eligible for inclusion in this study have to fulfill **all** of the following criteria:

1. Patient must be able to understand and communicate with the investigator and comply with the requirements of the study and must give a written, signed and dated informed consent before any study assessment is performed
2. Male or non-pregnant, non-lactating female patients at least 18 years of age
3. Diagnosis of PsA classified by CASPAR criteria and with symptoms for at least 6 months with moderate to severe PsA who must have had at Baseline ≥ 3 tender joints out of 78 and ≥ 3 swollen joints out of 76 (dactylitis of a digit counts as one joint each)
4. A target psoriatic skin lesion and a PASI score of 1 or greater
5. RF and/or Anti-cyclic citrullinated peptide (anti-CCP) antibodies negative at screening.
6. Patients who are regularly taking NSAIDs as part of their PsA therapy are required to be on a stable dose for at least 2 weeks before study randomization and should remain on a stable dose up to Week 16
7. Patients taking corticosteroids should be on a stable dose of ≤ 10 mg/day prednisone or equivalent for at least 2 weeks before randomization and must remain on a stable dose up to Week 16
8. Patients taking MTX (≤ 25 mg/week) are allowed to continue their medication if the dose is stable for at least 4 weeks before randomization and must remain on a stable dose up to study completion
9. Patients on MTX must be on folic acid supplementation at randomization
10. Patients who are on a DMARD other than MTX must discontinue the DMARD 4 weeks prior to randomization visit except for leflunomide, which should be discontinued for 8 weeks prior to randomization unless a cholestyramine washout has been performed.

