12.8 Appendix 8: Health Assessment Questionnaire (HAQ)

The HAQ[®] (Fries JF et al. 1980) is a validated measure of physical disability and functional status. It has four dimensions: disability, pain, drug side effects and dollar costs, although, the latter three are rarely used in clinical trials. In this trial only the disability dimension will be used. The disability dimension consists of 20 multiple choice items concerning difficulty in performing eight common activities of daily living; dressing and grooming, arising, eating, walking, reaching, personal hygiene, gripping and activities. Patients choose from four response categories, ranging from 'without any difficulty' to 'unable to do'. The ACR Rheumatology Committee on Outcome Measures in RA recommends the use of this questionnaire in clinical trials.

Scoring of the HAQ[®]

The HAQ[®] will be scored in accordance with the recommendation from the developers outlined in the "HAQ PACK" from Stanford University, California.

The following coding is to be used for the 8 categories of the disability outcome dimension:

Without ANY Difficulty	0
With SOME Difficulty	1
With MUCH Difficulty	2
UNABLE to do	3

Within each of the 8 categories only the item indicating the most severe impairment contributes to the category score. If the patient requires the use of aids, devices, or help from another to accomplish any of the activities in an associated category, then the score for that category will be assigned the value 2, unless the score is already 3 (i.e. scores of 0 or 1 are increased to 2). Associated categories are defined in the "HAQ PACK". From the scores for each category a Standard Disability Index (SDI) is computed by summing the computed scores for each category and dividing by the number of categories answered. The SDI is not

[figure not shown]
computed if the patient does not have scores for at least 6 categories. This SDI is the HAQ[®] score, which will be used in the statistical analyses of this instrument. The range for this score is (0, 3).

HAQ[®] Data Collection

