2.2.1 Subgroup of interest

Planned subgroups of interest are the subsets defined in Section 2.2.

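### SAP 2.11 defines both binary HAQ-DI variables without a baseline condition: patients already at 0.5 or below can count as responders, and patients below 0.35 cannot reach the MCID (minor)

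*SAP*

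**What the plan says.** SAP 2.11 adds two binary variables to the continuous HAQ-DI analysis. The first is "HAQ-DI response, where response = yes if HAQ-DI score ≤ 0.5". The second is "HAQ-DI MCID, where response = yes if HAQ-DI change from baseline <= -0.35". Neither carries a baseline condition. The section states that "All HR-QoL variables will be evaluated based on FAS patients", and the logistic model for both variables contains treatment, methotrexate use and body weight, but not baseline HAQ-DI. The SAP also plans that "number and percentages will be provided for HAQ-DI responders by treatment group at each visit for entire treatment period", with a parallel version under non-responder imputation.

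No HAQ-DI subset exists. SAP 2.2.1 says "Planned subgroups of interest are the subsets defined in Section 2.2", and the disease-based subsets there concern psoriasis, dactylitis and up-titration. On disease activity, Protocol 4.1 asks for "≥ 3 tender joints out of 78 and ≥ 3 swollen joints out of 76", together with CASPAR classification, symptom duration and a PASI of at least 1. None of the inclusion or exclusion criteria sets a HAQ-DI minimum.

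Elsewhere the study does apply baseline conditions. PASI responses are analysed in patients with at least 3% of body surface affected at baseline (SAP 2.7.2). Dactylitis and enthesitis are analysed in patients who have them at baseline (SAP 2.7.2). An IGA 0 or 1 responder must also improve by at least 2 points (Protocol 6.4.15).

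**The concern.** The word response implies that something changed. Under the first rule nothing has to change: a patient at 0 at baseline and 0.5 at Week 16 has worsened by 0.5 and is still a responder. Under the second rule some patients are counted as failures although the scale gives them no room to succeed. One low-baseline patient can be a responder on the first variable and a certain non-responder on the second.

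The by-visit counts to Week 52 are the most exposed. Placebo patients move to secukinumab 300 mg from Week 16 (Protocol 3.1), so later percentages have no concurrent control to show how much of the rate was there at the start. Adding baseline HAQ-DI to the Week 16 model would not alter these counts.

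**Working it through.** **The plan's own figures.** The documents give no HAQ-DI rate, variance or power to reproduce. Their only calculated sample size is for ACR20: 20% v 50%, 2:1 allocation, continuity correction. It reproduces at 44 and 88 and does not bear on this point.

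**Step 1: attainable scores (documents only).** Protocol Appendix 8 builds the score as the sum of category scores (0 to 3 each) divided by the number of categories answered. At least 6 of 8 are needed, and the score runs from 0 to 3. With all 8 answered, the step is 1/8 = 0.125.
- Already at or below 0.5: 0, 0.125, 0.25, 0.375 and 0.5.
- MCID requires 0 − b ≤ −0.35, so b ≥ 0.35. Baselines of 0, 0.125 and 0.25 cannot meet it. The lowest that can is 0.375 (0.375 to 0 is −0.375).
- With 7 categories answered, 2/7 = 0.286 also cannot; with 6, 2/6 = 0.333 also cannot.

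**Step 2: how many patients (assumptions).** Assume baseline HAQ-DI is normal with mean μ of 1.0 to 1.3 and SD 0.6, recorded in steps of 0.125. A recorded 0.5 or less then means an underlying value below 0.5625, and a recorded 0.25 or less means one below 0.3125.

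| μ | At or below 0.5: Φ((0.5625 − μ)/0.6) | Cannot meet MCID: Φ((0.3125 − μ)/0.6) |
|---|---|---|
| 1.00 | Φ(−0.729) = 23% | Φ(−1.146) = 13% |
| 1.15 | Φ(−0.979) = 16% | Φ(−1.396) = 8% |
| 1.30 | Φ(−1.229) = 11% | Φ(−1.646) = 5% |

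If nothing changes between visits except measurement noise, the distribution at Week 16 is the same as at baseline. The no-effect response rate is therefore also 11 to 23%.

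**Step 3: effect on the Week 16 comparison (simulation).** Further assumptions: within-patient visit SD 0.20 to 0.28 (within the total SD of 0.6), mean change −0.15 on placebo and −0.42 on drug, between-patient SD of change 0.35, and 100 v 50 patients. The middle case is mean 1.15 and visit SD 0.24.

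| Variable, population | Drug | Placebo | Difference | Power |
|---|---|---|---|---|
| ≤0.5, all | 40% | 26% | 14 points | about 39% |
| ≤0.5, baseline >0.5 | 31% | 17% | 14 points | about 37 to 38% |
| MCID, all | 55% | 35% | 20 points | about 64% |
| MCID, baseline ≥0.35 | 60% | 38% | 22 points | about 68% |

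The MCID rows are linked exactly: rate in those able to respond = rate in all / (1 − share unable). With 8% unable, 55/0.92 = 60 and 35/0.92 = 38. Over all scenarios the MCID restriction adds about 2 to 6 points of power. Restricting the 0.5 threshold moves its difference by only about −0.5 to +1 point. Of drug patients at or below 0.5 at Week 16, 28 to 43% were there at baseline.

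**Step 4: sensitivity for the 0.5 threshold.** The result depends on whether drug helps low-baseline patients stay low. Take 15% v 35% among those starting above 0.5, a difference of 20 points, with 20% of patients already at or below 0.5.
- Equal 90% retention: 0.2×0.90 + 0.8×0.15 = 30% v 0.2×0.90 + 0.8×0.35 = 46%, a difference of 16 points.
- Retention 80% v 95%: 0.2×0.80 + 0.8×0.15 = 28% v 0.2×0.95 + 0.8×0.35 = 47%, a difference of 19 points.

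Dilution of this difference is thus possible if drug has no effect on retention, but it does not follow from the definition alone.

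**The case against.** The strongest reply is that a score of 0.5 or less is a recognised state, not a change. The same threshold is a component of Minimal Disease Activity (Protocol 6.4.10), where it has no baseline condition of its own. A state measure should count patients who remain in the state. The SAP pairs it with a change measure and with the continuous HAQ-DI analysis, which is the listed secondary variable and adjusts for baseline. SAP 2.1 also asks for change from baseline by visit for continuous variables, and Table 2-1 lists Baseline as an analysis visit, so a by-visit table might show the starting percentage. All of this stands. It reduces the point on the 0.5 threshold to the label and to a baseline percentage that the SAP does not explicitly require. It does not answer the MCID point, because no presentation lets a patient at 0.25 fall by 0.35.

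A reader might infer three stronger things.
- **That the Week 16 comparisons are biased.** They are not: baseline HAQ-DI precedes treatment, and randomisation balances low-baseline patients on average.
- **That patients already at 0.5 or below dilute the Week 16 difference.** They raise the rate in every arm, but the difference stays at about 14 points in the middle case, and restriction gains no power.
- **That the definitions were chosen to flatter the results.** The SAP revision history lists these variables in a December 2018 entry for the Week 52 analysis, after the Week 16 lock. It says nothing about why the rules took this form.

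SAP 2.13 is not in the public text, so a restriction there cannot be excluded. None appears where the variables are defined.

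**Conclusion.** The point holds and is minor. From the documents alone, baselines of 0.5 or less already satisfy the response rule, and baselines below 0.35 can never satisfy the MCID rule. Patients already at 0.5 or below still count only if they remain there and, under non-responder imputation, have data at the visit.

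For the 0.5 threshold, the harm is an inflated and misnamed responder rate, mainly in the uncontrolled summaries to Week 52. For MCID, rates and differences are diluted in proportion to the share unable to respond, by about 2 points of difference in the middle case. Every percentage rests on the assumed distribution and changes in the working, since the documents supply none. Both variables lie outside the 12 listed secondary variables, and ACR20 and the sample size are untouched.

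**What to change.** In SAP 2.11:

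1. Analyse HAQ-DI MCID in FAS patients with baseline HAQ-DI of at least 0.35, for both the models and the by-visit summaries.
2. Keep HAQ-DI of 0.5 or less in the FAS, described as an attained state rather than a response, and show the baseline percentage by arm beside the later visits.
3. Add the response analysis and by-visit summaries for patients with baseline HAQ-DI above 0.5.
4. Report the number excluded per arm for each restricted analysis.

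The filters use pre-treatment data already collected, so the randomised comparison at Week 16 is kept. The cost is SAP wording and a smaller sample: about 5 to 13% fewer for MCID and 11 to 23% fewer for the 0.5 response. The restricted 0.5 rates will be lower, with no gain in power. Restriction also leaves some regression to the mean: about 4 to 11% would still cross to 0.5 or below with no effect, under the same assumptions. The Week 52 percentages therefore remain uncontrolled and should be described as such.

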2.5.2 Statistical hypothesis, model, and method of analysis

Let π_i denote the probability of an ACR20 response at Week 16 for treatment group j, j = 0, 1, 2, where 0 corresponds to placebo, 1 corresponds to secukinumab 150 mg, and 2 corresponds to secukinumab 300 mg. Accordingly, $\pi_i/(1 - \pi_i)$ is the odds for treatment group j, j = 0, 1, 2.

The following null hypotheses (H_{01} and H_{02}) will be tested against their corresponding alternative hypotheses (H_{A1} and H_{A2}):

 $H_{01}: [\pi_1/(1-\pi_1)]/[\pi_0/(1-\pi_0)] \le 1$ versus $H_{A1}: [\pi_1/(1-\pi_1)]/[\pi_0/(1-\pi_0)] > 1$

H₀₂: $[\pi_2/(1-\pi_2)]/[\pi_0/(1-\pi_0)] \le 1$ versus H_{A2}: $[\pi_2/(1-\pi_2)]/[\pi_0/(1-\pi_0)] > 1$

The primary efficacy variable will be analyzed at Week 16 using a logistic regression model with treatment (3 treatment groups), methotrexate usage at baseline (yes, no), and body weight (in kg) as explanatory variables (Stokes, Davis, and Koch, 2012). The odds ratios for each dose of secukinumab versus placebo, 95% confidence intervals for the odds ratios, and p-values based on the fitted model will be reported. If the p-value for a dose of secukinumab versus placebo is < 0.05 and the corresponding odds ratio is greater than 1, statistical significance in favor of that dose of secukinumab is shown.

Methotrexate usage at baseline and body weight are assumed to have possible impact on the variable, so those will be included in the logistic regression model, even though the factors will not be used to stratify at randomization.

The primary variable will also be analyzed at each time point till Week 16 using the same model.

Number and percentages of ACR20 responders will be reported for each treatment group by visit in entire treatment period up to Week 52 using oberved data. Similar summary will be provided for ACR20 using non-responder imputation.

Number and percentages of ACR20 responders will be reported for each treatment group, concomitant methotrexate usage at baseline and by visit in entire treatment period up to Week 52. Similar summary will be provided for ACR20 using non-responder imputation.

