2.7.2 Statistical hypothesis, model, and method of analysis

Dactylitis and enthesitis

Analyses of dactylitis and enthesitis will be performed at each time point up to Week 16. The data for the subgroup of patients who have dactylitis at baseline (similarly for enthesitis) will be used and the data will be analyzed using a logistic regression model with treatment (3 treatment groups), methotrexate usage at baseline (yes, no), and body weight as explanatory variables. The odds ratios for each dose of secukinumab versus placebo, 95% confidence interval for the odds ratios, and p-values based on the fitted model will be reported.

Number and percentages of patients with presence of enthesitis will be reported for each treatment group and by visit in entire treatment period up to Week 52. Similar summary will be provided for patients with presence of enthesitis using non-responder imputation.

The above analyses will be done on Dactylitis Subset,

ACR20, ACR50, and ACR70 responses

ACR20, ACR50, ACR70 responses at each time point up to Week 16, and in subsets of patients with active PsA and number of tender and swollen joints < 10 and ≥ 10 at baseline will be analyzed using a logistic regression model with treatment (3 treatment groups), methotrexate usage at baseline (yes, no), and body weight as explanatory variables. The odds ratios for each dose of secukinumab versus placebo, 95% confidence intervals for the odds ratios, and p-values based on the fitted model will be reported.

Additionally, ACR50 and ACR70 responses will be analyzed as analogous to primary efficacy variable at each time point up to Week 16.

Number and percentages of ACR50 and ACR70 responders will be reported for each treatment group, concomitant methotrexate usage at baseline and by visit in entire treatment period up to Week 52. Similar summary will be provided for ACR50 and ACR70 using non-responder imputation.

Number and percentages of ACR50 and ACR70 responders in subsets of patients with active PsA and number of tender and swollen joints < 10 and \geq 10 at baseline will be reported for each treatment group and by visit in entire treatment period up to Week 52. Similar summary will be provided for ACR50 and ACR70 using non-responder imputation.

Minimal Disease Activity

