Minimal Disease Activity response at each time point up to Week 16 will be analyzed using a logistic regression model with treatment (3 treatment groups), methotrexate usage at baseline (yes, no), and body weight as explanatory variables. The odds ratios for each dose of secukinumab versus placebo, 95% confidence intervals for the odds ratios, and p-values based on the fitted model will be reported.

Number and percentages of Minimal Disease Activity response will be reported for each treatment group and by visit in entire treatment period up to Week 52. Similar summary will be provided for Minimal Disease Activity response using non-responder imputation method.

Very Low Disease Activity

Very Low Disease Activity (yes, no) is achived when 7 out of the following 7 criteria are met: ≤ 1 tender joint, ≤ 1 swollen joint, PASI ≤ 1 or IGA mod 2011 ≤ 1 , patient assessment of pain (0-100 Visual Analog Scale (VAS)) ≤ 15 , patient global assessment of disease (VAS) ≤ 20 , HAQ-DI ≤ 0.5 , tender entheseal points ≤ 1 .

Very Low Disease Activity response at each time point up to Week 16 will be analyzed using a logistic regression model with treatment (3 treatment groups), methotrexate usage at baseline (yes, no), and body weight as explanatory variables. The odds ratios for each dose of secukinumab versus placebo, 95% confidence intervals for the odds ratios, and p-values based on the fitted model will be reported.

Number and percentages of Very Low Disease Activity response will be reported for each treatment group and by visit in entire treatment period up to Week 52 for the observed data. Similar summary will be provided for Very Low Disease Activity response using non-responder imputation method.

PASI75, PASI90, PASI100 responses

Response to PASI75, PASI90, PASI100 at each time point up to Week 16 will be analyzed using a logistic regression model with treatment (3 treatment groups), methotrexate usage at baseline (yes, no), and body weight as explanatory variables. The odds ratios for each dose of secukinumab versus placebo, 95% confidence intervals for the odds ratios, and p-values based on the fitted model will be reported.

Novartis	For business use only	Page 28
SAP		Secukinumab/AIN457FUS01

The above analyses will be done on Psoriasis Subset.

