5.4.3 Secondary analysis

Categorical variables will be analyzed using the logistic model, using the code described above.

Continuous variables will be analyzed using an analysis of covariance (ANCOVA) model with treatment, baseline value, methotrexate usage at baseline (yes, no), and body weight as explanatory variables.

Proc mixed data=aaa order=internal; Class TRT MTX; Model change=TRT MTX BLV weight/ ddfm=kr; Lsmeans TRT/ cl diff; Contrast "sec300 vs plb" TRT 1 0 -1/ cl diff alpha=0.05; Contrast "sec150 vs plb" TRT 0 1 -1/ cl diff alpha=0.05; Run;

For supportive analysis using Cochran-Mantel-Haenszel (CMH) test to compare treatments adjusting for methotrexate usage at baseline, the same code will be used as described above.

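### SAP 2.11 sets no Week 16 limit on the placebo odds ratios for the two HAQ-DI responder variables; as a lesser matter, both models leave out baseline HAQ-DI

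*SAP*

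**What the plan says.** SAP 2.11 defines two binary HAQ-DI variables: a score of 0.5 or less, and a change from baseline of -0.35 or lower (MCID). For both it says: "The above analysis will be done at each time point using a logistic regression model with treatment (3 treatment groups". Methotrexate use and body weight are the other covariates, and the output is an odds ratio, 95% confidence interval and p-value for each dose against placebo. No last visit is named.

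The neighbouring text is narrower:
- HAQ-DI total score, just before: "Analysis of HAQ-DI total score will be analogous to the analysis of SF12 for all time points up to Week 16". The SF12 model that it copies includes the "baseline SF12 score, methotrexate usage at baseline (yes, no), and body weight as explanatory variables".
- Descriptive summary, just after: "number and percentages will be provided for HAQ-DI responders by treatment group at each visit for entire treatment period".
- ACR20 (SAP 2.5.2): "The primary variable will also be analyzed at each time point till Week 16 using the same model".
- Dactylitis and enthesitis (SAP 2.7.2): "Analyses of dactylitis and enthesitis will be performed at each time point up to Week 16".
- Very low disease activity (SAP 2.7.2): "Very Low Disease Activity response at each time point up to Week 16 will be analyzed using a logistic regression model".

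On covariates, SAP 5.4.3 sets the convention for binary variables: "Categorical variables will be analyzed using the logistic model, using the code described above". That code has treatment, methotrexate and weight, and no baseline score.

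**The concern.** SAP 1.1 moves every placebo patient to secukinumab 300 mg from Week 16, whatever their response, and moves 150 mg non-responders to 300 mg at Week 16, 28 or 40. After Week 16 no group is on placebo. SAP 2.2 analyses efficacy by randomised arm, so the three-group model would still run at later visits with the switched patients labelled placebo. As those patients respond, the odds ratio moves towards 1, and a reader could take this for loss of effect.

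The second matter is efficiency. The 0.5 threshold carries no baseline condition, so some patients may meet it at entry, and MCID is itself a change from baseline. Baseline HAQ-DI can therefore predict either outcome. It is already collected and already used for the total score, and the comparator is a planned arm of only 50.

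**Working it through.** **Part 1: the time limit**

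The placebo-comparison models in SAP 2.5, 2.7 and 2.11, side by side:

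| Variable | Section | Stops at Week 16? |
|---|---|---|
| ACR20 logistic; CMH | 2.5.2; 2.5.4 | yes |
| Dactylitis, enthesitis, ACR20/50/70, MDA, VLDA, PASI | 2.7.2 | yes |
| DAS28-CRP, PASDAS | 2.7.2 | yes |
| SF12, HAQ-DI total score | 2.11 | yes |
| HAQ-DI ≤0.5, HAQ-DI MCID | 2.11 | not stated |

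Very low disease activity (VLDA) is the closest comparator. It too is outside the 12 listed secondaries and appears in the same post-lock entry of the SAP's update history, yet its model has the limit.

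Does a general rule close the gap? SAP 2.1 (Comparative efficacy data) focuses placebo comparisons on the first 16 weeks, but allows inference from Week 16 to Week 52 where specified. SAP 5.4.1 applies logistic regression at each visit. Neither excludes the literal reading.

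Number affected on that reading: 2 variables × 2 doses = 4 odds ratios per later visit with HAQ-DI. The total depends on the HAQ-DI row of protocol Table 6-1, which is not in the text available.

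Size of the drift, by simulation (10,000 trials; arms 100/100/50; 10% counted as non-responders; the SAP's model). All HAQ-DI inputs are assumed:
- Case A: baseline mean 1.2, SD 0.6; mean change -0.15 placebo, -0.45 active; SD of change 0.45.
- Case B: 1.3, 0.65; -0.15, -0.40; 0.5; mean change proportional to baseline.

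After the switch, the former placebo arm's mean change = placebo change + f × (active change - placebo change). In case A with f = 0.8: -0.15 + 0.8 × (-0.30) = -0.39.

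| Gap closed (f) | A: ≤0.5 | A: MCID | B: ≤0.5 | B: MCID |
|---|---|---|---|---|
| 0 (Week 16) | 1.96 | 2.59 | 1.64 | 2.10 |
| 0.5 | 1.39 | 1.58 | 1.29 | 1.41 |
| 0.8 | 1.14 | 1.19 | 1.12 | 1.14 |
| 1.0 | 1.00 | 1.00 | 1.01 | 1.00 |

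(median odds ratios)

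**Part 2: baseline HAQ-DI**

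The plan's only sizing is for ACR20 (SAP section 3: 50% against 20%, 2:1, two-sided 0.05, 90% power, continuity-corrected), and it reproduces:
- Pooled rate = (0.2 + 2 × 0.5)/3 = 0.4.
- n = [1.96√(1.5 × 0.4 × 0.6) + 1.2816√(0.16 + 0.25/2)]²/0.3² = 38.45.
- Corrected n = (38.45/4)[1 + √(1 + 6/(38.45 × 2 × 0.3))]² = 43.3, so 44 placebo and 88 active. Dividing by 0.9 gives 49 and 98, planned as 50 and 100.

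No power is claimed for the HAQ-DI variables, so this too was simulated (2,000 trials per row). Assumptions: baseline normal, rounded to 0.125, limited to 0–3; Week 16 score = mean - 0.10 + ρ(baseline - mean) + SD√(1 - ρ²)z - effect, with effect 0.30 for 300 mg and 0.24 for 150 mg; 10% non-response. The test is |b/SE| > 1.96 for 300 mg against placebo. Power in %, without → with baseline:

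| Mean/SD | ρ | ≤0.5 | Gain | MCID | Gain |
|---|---|---|---|---|---|
| 1.2/0.65 | 0 | 41.3 → 41.4 | 0.1 | 24.9 → 34.1 | 9.2 |
| | 0.3 | 41.4 → 43.5 | 2.1 | 33.2 → 41.4 | 8.2 |
| | 0.5 | 43.3 → 49.1 | 5.8 | 44.1 → 50.4 | 6.3 |
| | 0.7 | 42.1 → 56.5 | 14.4 | 64.8 → 70.0 | 5.2 |
| | 0.8 | 41.7 → 63.1 | 21.4 | 80.4 → 83.9 | 3.5 |
| 1.0/0.60 | 0 | 53.4 → 53.3 | -0.1 | 29.2 → 39.6 | 10.4 |
| | 0.3 | 55.0 → 58.0 | 3.0 | 37.4 → 46.5 | 9.1 |
| | 0.5 | 54.3 → 59.0 | 4.7 | 48.2 → 54.9 | 6.7 |
| | 0.7 | 54.3 → 67.1 | 12.8 | 67.1 → 73.8 | 6.7 |
| | 0.8 | 53.9 → 73.6 | 19.7 | 83.5 → 87.1 | 3.6 |

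Further runs with the same kind of model gave gains as low as 1 (ρ = 0.3), 4 (0.5) and 11 (0.7) for ≤0.5, and 5 for MCID at ρ of 0.5 or less. Effect size matters too: at ρ = 0.7 and mean 1.2, an effect of 0.20 gives 20.3 → 26.5 for ≤0.5, and 0.40 gives 68.0 → 82.4.

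Case A, whose inputs imply a placebo correlation of about 0.76–0.77, gives 37 → 53 for ≤0.5 and 75 → 75 for MCID. Case B gives 18 → 23 and 53 → 56.

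With no treatment effect, the rejection rate for ≤0.5 was 4.4% without baseline and 5.2% with it.

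The adjusted odds ratio is a different quantity. In case A for ≤0.5 the median goes from 1.96 to 2.80 and the SE of the log odds ratio from 0.41 to 0.51. The ratio of upper to lower limit goes from exp(2 × 1.96 × 0.41) = 5.0 to exp(2 × 1.96 × 0.51) = 7.4. The SD of the standardised risk difference falls from 7.5 to 6.2 points.

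**The case against.** On part 1, the intent is fairly clear. SAP 2.1 points placebo inference to the first 16 weeks. SAP 2.4.1 lists no plain placebo group for the entire-period efficacy tables, only the placebo-to-300 mg group, so output that follows it would show the switch. The sentence before the models stops at Week 16, and the paragraph after them provides counts for the whole period. The each-visit line in SAP 5.4.1 is general code text under the primary analysis. All of this stands as evidence of intent. A reader might infer that the SAP means to test against placebo to Week 52; the documents do not support that. They only fail to exclude it.

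On part 2, the covariate set is a consistent convention, the variables are not listed secondaries, no power was promised for them, and change in HAQ-DI already has a baseline-adjusted ANCOVA. The covariate would also be added after the analysis statisticians were due to be unblinded at the Week 16 lock (SAP 2.1), which invites the charge of data-driven model choice. This stands as a reason to keep the current model and show the adjusted one beside it. It does not remove the possible power cost.

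**Conclusion.** The missing limit is a real gap, with a one-phrase remedy. As written, the sentence can produce odds ratios labelled against placebo when nobody is on placebo: four per later HAQ-DI visit, drifting to 1 as switched patients catch up.

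The missing baseline covariate is a secondary efficiency point that rests on assumed inputs. For ≤0.5 the gain is about 0 points at correlation 0, 1 to 3 at 0.3, 4 to 6 at 0.5 and 11 to 21 at 0.7 to 0.8 with an effect of 0.30 (about 5 or 6 with the weaker effects tried). For MCID it is about 5 to 10 points at 0 to 0.5 and 0 to 7 at 0.7 to 0.8.

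Two stronger readings should be resisted. One is that leaving out baseline biases the Week 16 test or contradicts the total-score ANCOVA: the null rejection rates and SAP 5.4.3 say otherwise. The other is that the cost falls on ≤0.5 and spares MCID: that holds only at high correlation, and at 0.5 or below MCID gains at least as much.

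Minor overall.

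**What to change.** In SAP 2.11:
1. Limit the two HAQ-DI logistic models to time points up to Week 16, and keep later visits to the counts and percentages already planned there. This costs one phrase.
2. For both variables, report a model with baseline HAQ-DI added beside the current model. Label it as added after the Week 16 database lock, and state that its odds ratio is conditional on baseline, lies further from 1 and has a wider interval. The gain is in power and risk-difference precision. This needs one covariate and no new data. The price is a departure from the binary-model convention in SAP 5.4.3 and a visible post-lock addition.
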